9.5 Halting Rules

Additional enrollment and study interventions/administration of study products in this trial will be halted for DSMB review/recommendation if any of the following are reported:

- Any subject experiences ulceration, abscess or necrosis at the injection site that is considered related to study product administration.

- Any 2 or more subjects experience laryngospasm, bronchospasm or anaphylaxis within 1 day after administration of study product that is considered related to study product.
- Three or more subjects experience generalized urticaria (defined as occurring at more than two body parts) within 3 days after administration of study product that is considered related to study product.
- Any subject experiences an SAE after administration of study product that is considered related to study product.
- Any subject experiences acute weakness of limbs and/or cranial nerve innervated muscles (description of potential signal of GBS) after administration of study product.
- Any subject develops a PIMMC after administration of study product.

This trial will also be halted for DSMB review/recommendation if, within 7 days after administration of study vaccination, any of the following occurs:

- 7% or more of subjects (with a minimum of 3 subjects) who received a dose of study vaccine experience the same severe (Grade 3) study vaccine-related injection site reaction. Ecchymosis, erythema and induration (hardness)/edema (swelling) will also be measured in mm but size will not be used as halting criteria.
- 7% or more of subjects (with a minimum of 3 subjects) who received a dose of study vaccine experience the same severe (Grade 3) study vaccine-related subjective systemic reaction, for which the severity (grade) is corroborated by study personnel.
- 7% or more of subjects (with a minimum of 3 subjects) who received a dose of study vaccine experience the same severe (Grade 3) study vaccine-related quantitative systemic reaction.
- 7% or more of subjects (with a minimum of 3 subjects) who received a dose of study vaccine experience the same severe (Grade 3) study vaccine-related clinical safety laboratory AE.

Grading scales for solicited injection site and systemic (subjective and quantitative) reactions are included in [Section 9.2.2](#).

Grading scales for clinical safety laboratory AEs are included in [Section 9.2.3](#).

If any of the halting rules are met following any subject receipt of study vaccination, then this trial will not continue with the remaining enrollments without a review by and recommendation from the DSMB to proceed.

DMID retains the authority to suspend additional enrollment and study interventions/administration of study products during this trial, as applicable.

The DMID Medical Monitor is empowered to stop enrollment and study vaccinations if AEs that meet the halting criteria are reported.

9.6 Safety Oversight

9.6.1 Independent Safety Monitor (ISM)

An ISM is a physician with relevant expertise whose primary responsibility is to provide to DMID an independent safety assessment in a timely fashion. This is a voluntary position that does not receive payment. The ISM must meet the requirements of the NIAID Conflict of Interest (COI) policy.

For this clinical trial an ISM is not required. However, at each participating VTEU site, **upon DMID Medical Monitor request**, the site PI will identify a physician with relevant expertise, to act as a Secondary Medical Assessor (SMA). The SMA will examine a subject and/or medical records and provide to DMID a medical assessment (or second medical opinion) of the safety event in question. The site PI or appropriate sub-investigator will send to the DMID Medical Monitor, a summary of the event and include the site PI or appropriate sub-investigator and SMA assessments.

Note: In the case that DMID has requested this type of evaluation multiple times, DMID may request the participating VTEU site(s) identify an ISM to assist DMID with safety oversight, and then the below requirements will apply.

The ISM:

- Is in close proximity to the study site and has the authority and ability to readily access subject records in real time.
- May be a member of the participating VTEU site's staff, but preferably be from a different organizational group within the institution.
- Should not be in a direct supervisory relationship with the site PI.

- Should have no direct involvement in the conduct of the study.

The ISM will:

- Sign a COI certification at the time he/she is asked to participate and provide updates to this information as needed.
- Receive reports of SAEs from the site PI or appropriate sub-investigator and will be notified by email when DMID is notified of the SAE.
- Evaluate the SAE and report his/her clinical assessment to DMID in a timely manner.
- Communicate with the site PI or appropriate sub-investigator at the participating VTEU site as needed.
- Review additional safety related events at the request of DMID.
- Provide additional information to DMID and/or the DSMB by teleconference as requested.

9.6.2 Data and Safety Monitoring Board (DSMB)

Safety oversight will be conducted by a DSMB that is an independent group of experts that monitors subject safety and advises DMID. The DSMB members will be separate and independent of study personnel participating in this trial and should not have scientific, financial or other COI related to this trial. The DSMB will consist of members with appropriate expertise to contribute to the interpretation of the data from this trial.

The DSMB will operate under the rules of a DMID-approved charter that will be written at the organizational meeting of the DSMB. At this time, each data element that the DSMB needs to assess will be clearly defined. Procedures for DSMB reviews/meetings will be defined in the charter. The DSMB will review applicable data to include, but not limited to, study progress and subject, clinical, safety, reactogenicity, and immunogenicity data. Reports may include enrollment and demographic information, medical history, concomitant medications, physical assessments, clinical laboratory values, dosing compliance, solicited and unsolicited AE/SAEs, and HAI and Neut antibody assay results. The DSMB will review SAEs on a regular basis and ad hoc during this trial. The DMID Medical Monitor and the ISM (as deemed necessary) will be responsible for reviewing SAEs in real time.

The DSMB will conduct the following reviews:

- Data review for safety at trial-specific time frames; at least annually.

- Electronic review when 8-day reactogenicity and clinical safety laboratory data following study vaccination is available for 25% of study subjects.
- Data review when 8-day reactogenicity and clinical safety laboratory data following study vaccination is available for 75% of study subjects.
- Ad hoc when a halting rule is met, or DMID/DSMB chair may convene an ad hoc meeting if there are immediate concerns regarding observations during the course of this trial. The DMID Medical Monitor is empowered to stop enrollment and study vaccinations if AEs that meet the halting criteria are reported.
- Final review meeting may be held 6 to 8 months after clinical database lock to review the cumulative unblinded safety and immunogenicity data for this trial. If a final review meeting is held, the data will be provided in a standard summary format. The DSMB may be asked to provide recommendations in response to questions posed by DMID.

Additional data may be requested by the DSMB, and interim statistical reports may be generated as deemed necessary and appropriate by DMID. The DSMB may receive data in aggregate and presented by treatment arm. The DSMB may also be provided with expected and observed rates of the expected AEs in an unblinded fashion, and may request the treatment assignment be unblinded for an individual subject if required for safety assessment. The DSMB will review grouped and unblinded data in the closed session only. As an outcome of each review/meeting, the DSMB will make a recommendation as to the advisability of proceeding with study vaccinations, as applicable, and to continue, modify or terminate this trial.

10 CLINICAL MONITORING

10.1 Site Monitoring Plan

Site monitoring is conducted to ensure that the human subjects' protections, study and laboratory procedures, study interventions/administration of study products, and data collection processes are of high quality and meet sponsor and ICH E6 GCP guidelines and applicable federal regulations, and that this trial is conducted in accordance with the protocol, protocol-specific MOP and applicable sponsor SOPs. DMID, the sponsoring agency, or its designee will conduct site-monitoring visits as detailed in the clinical monitoring plan. DMID-designated clinical monitors will verify that this trial is conducted and data are generated, documented (recorded) and reported in compliance with the protocol, ICH E6 GCP guidelines and applicable regulatory requirements. Clinical monitoring reports will be submitted to DMID.

Site visits will be made at standard intervals as defined by DMID and may be made more frequently as directed by DMID. Monitoring visits will include, but are not limited to, review of regulatory files, accountability records, eCRFs, ICFs, medical and laboratory reports, and protocol and GCP compliance. Site monitors will have access to each participating VTEU site, study personnel and all study documentation according to the DMID-approved site monitoring plan. Study monitors will meet with site PIs to discuss any problems and actions to be taken and document visit findings and discussions.

11 STATISTICAL CONSIDERATIONS

11.1 Introduction

The goal of this clinical trial is to assess the safety, reactogenicity, and immunogenicity of a single boosting dose of 2017 A/H7N9 IIV with or without AS03 adjuvant in subjects who received 2013 A/H7N9 IIV in previous trials (DMID Protocols 13-0032 and 13-0033) and subjects who are A/H7 IIV-naïve. These treatment arms are included to allow evaluation of the priming effect of the 2013 A/H7N9 IIV given with/without adjuvant to enhance the immune response to the 2017 A/H7N9 IIV. Additional goals are to investigate novel methods for identifying and assessing alternative serological correlates of protection against influenza infection.

11.2 Study Hypotheses

This Phase II study is not designed to test a formal null hypothesis. Rather, it is intended to obtain sufficient data to obtain meaningful estimates of the immune response induced by this vaccine and to uncover any safety issues that occur at a sufficiently high rate that they might be observed in a study of this size. The sample size facilitates formal testing of selected hypotheses as discussed in [Section 11.4.3](#), along with the probability of observing safety outcomes and the precision of immunogenicity outcomes.

11.3 Study Outcome Measures

Please refer to Study Outcome Measures outlined in [Section 3.2](#).

11.4 Sample Size Considerations

Please refer to Study Design outlined in [Section 4](#).

11.4.1 Study Population

The study population for this clinical trial includes males and non-pregnant females, 19 to 70 years of age, inclusive, who are in good health and meet all eligibility criteria. The subjects will be recruited from the general population at each of the participating VTEU sites that have substantial experience conducting large influenza vaccine studies.

11.4.2 Subject Enrollment and Follow-up

Based on the accrual rates observed in similar studies, it seems reasonable to expect that the participating VTEUs will be able to enroll this trial in a timely fashion. In previous DMID trials, 7 VTEUs recruited 388 healthy subjects, 19 to 64 years of age, in 14 weeks. Prior experience suggests approximately 3% of subjects may be excluded from the per protocol (PP) analysis for the primary immunogenicity outcome either because they were lost-to-follow-up, or because they had a protocol deviation requiring their exclusion from the PP analysis.

Follow-up will consist of 2 segments. The first encompasses the core data for this trial and will consist of results for all study visits through approximately 21 days after study vaccination. The second segment consists of a 6-month immunogenicity assessment and follow-up safety assessments through approximately 12 months after study vaccination.

11.4.3 Sample Size

This study is planned to enroll up to 420 subjects. The majority of subjects will be recruited from the population of subjects who received the 2013 A/H7N9 IIV in DMID Protocols 13-0032 and 13-0033. The sample size for this study was selected using estimates of recruitment based on the number of subjects completing these historical protocols by 2013 A/H7N9 IIV vaccination history (summarized in Table 10).

Table 10: Previously Primed Subjects For Potential Enrollment in 17-0090

17-0090 Study Strata	2013 A/H7N9 IIV Protocol Treatment Arms	Dose 1	Dose 2	Completed All Visits	Able to recruit 50% Completers	Able to recruit 25% Completers
One or two doses 2013 A/H7N9 IIV with MF59	13-0032 Treatment Arms 1-3 13-0033 Treatment Arm 8	396	387	385	192	96
One or two doses 2013 A/H7N9 IIV with AS03	13-0033 Treatment Arms 1-3	291	278	279	137	70
One or two doses 2013 A/H7N9 IIV 15 mcg or 45 mcg unadjuvanted	13-0032 Treatment Arms 6-7 13-0033 Treatment Arms 9-10	396	383	383	191	95
2013 A/H7N9 IIV + MF59 or AS03 (1 st) then 2013 A/H7N9 IIV 15 mcg (2 nd)	13-0032 Treatment Arm 4 13-0033 Treatment Arm 4	199	190	193	96	48

While this study is not designed to test any specific null hypothesis, the following illustrates the precision and power that are available for select estimates and comparisons of interest.

Table 12 indicates the probability of observing one or more safety events, such as solicited injection site or systemic reactogenicity events or an unsolicited non-serious AE of a particular type for treatment arms (N=30, 50), in all subjects receiving adjuvant (N=210), or in the trial as a whole (N=420).

Table 11: Power (%) to Detect Safety Events

Event Frequency	N=30	N=50	N=210	N=420
≥10% Very Common	95	>99	>99	>99
≥1% Common	26	39	87	98
≥0.1% Uncommon	2	4	18	34
≥0.01% Rare	<1	<1	2	4

Binomial confidence intervals (CI) are widest (have the least precision) when the response rate is 50%.

Table 12 is presented to indicate the worst-case scenario for precision of observed exact (Clopper-Pearson) binomial confidence intervals.

Table 12: Precision of Binomial Confidence Intervals

N	95% CI
30	31-69
50	35-65
210	43-57
420	45-55

Table 13 illustrates the minimum detectable differences in the proportion of subjects responding (e.g. attaining seroconversion or a titer $\geq 1:40$) between any two treatment arms (N=30 or 50) using a two-sided Likelihood Ratio Test and alpha = 0.05.

From previous experience with single dose studies, it is assumed that up to 3% of subjects will be excluded from the per protocol analysis with minimal effect on these calculations. Seroconversion rates of 10% to 90% are considered.

Table 13: Minimum Detectable Difference in Proportion Responders

N per Treatment Arm	Proportion Responders in Comparator Group A	80% Power	
		Minimal Detectable Difference	Proportion Responders in Comparator Group B
N=30	0.10	0.29	0.39
	0.20	0.34	0.54
	0.30	0.35	0.65

	0.40	0.35	0.75
	0.50	0.33	0.83
	0.60	0.30	0.90
	0.70	0.25	0.95
	0.80	0.19	0.99
	0.90	0.10	>0.99
N=50	0.10	0.22	0.32
	0.20	0.26	0.46
	0.30	0.27	0.57
	0.40	0.27	0.67
	0.50	0.27	0.77
	0.60	0.25	0.85
	0.70	0.22	0.92
	0.80	0.17	0.96
	0.90	0.10	>0.99

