Reactogenicity will be measured by the occurrence of solicited injection site and systemic reactions from the time of study vaccination through 7 days after study vaccination. Unsolicited non-serious adverse events (AEs) will be collected from the time of study vaccination through approximately 21 days after study vaccination. Serious adverse events (SAEs) and medically-attended adverse events (MAAEs), including new-onset chronic medical conditions (NOCMCs) and potentially immune-mediated medical conditions (PIMMCs), will be collected from the time of study vaccination through approximately 12 months after study vaccination. Clinical safety laboratory evaluations (hematology and chemistry) will be performed on venous blood collected immediately prior to study vaccination and approximately 7 days after study vaccination.

Immunogenicity testing will include performing serological assays to assess hemagglutination inhibition (HAI), neutralizing (Neut), neuraminidase inhibition (NAI), neuraminidase (NA)-specific, and HA stem-specific antibody titers at multiple time points following each study vaccination. Venous blood will also be collected at multiple time points following study vaccination for the future research use of serum, plasma and peripheral blood mononuclear cells (PBMCs).

[figure not shown]
Correlation of the H7 HA and N9 NA-specific serum antibody responses to the inclusion of an adjuvant in the prime and/or boost regimens will also be determined.

Table 1: Study Design

2013 A/H7N9 IIV Vaccination History (Number of eligible subjects)	Treatment Arm/N	Study Vaccination Day 1
1 or 2 doses 2013 A/H7N9 IIV with MF59 (385)	1/50	2017 A/H7N9 IIV 3.75 mcg + AS03
	2/50	2017 A/H7N9 IIV 3.75 mcg
1 or 2 doses 2013 A/H7N9 IIV with AS03 (279)	3/50	2017 A/H7N9 IIV 3.75 mcg + AS03
	4/50	2017 A/H7N9 IIV 3.75 mcg
1 or 2 doses 2013 A/H7N9 IIV 15 mcg or 45 mcg unadjuvanted (383)	5/50	2017 A/H7N9 IIV 3.75 mcg + AS03
	6/50	2017 A/H7N9 IIV 3.75 mcg
2013 A/H7N9 IIV + MF59 or AS03 (1 st) then 2013 A/H7N9 IIV 15 mcg (2 nd) (193)	7/30	2017 A/H7N9 IIV 3.75 mcg + AS03
	8/30	2017 A/H7N9 IIV 3.75 mcg
A/H7 IIV-Naïve	9/30	2017 A/H7N9 IIV 3.75 mcg + AS03
	10/30	2017 A/H7N9 IIV 3.75 mcg
Total N = 420 - Previously Vaccinated with H7N9 (N = 360) and Not Previously Vaccinated with H7 (N = 60)		

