4 STUDY DESIGN

This is a Phase II clinical trial in up to 420 males and non-pregnant females, 19 to 70 years of age, inclusive, who are in good health and meet all eligibility criteria, which include a screening erythrocyte sedimentation rate (ESR) laboratory evaluation. This clinical trial is designed to assess the safety, reactogenicity and immunogenicity of one dose of a monovalent inactivated split influenza 2017 A/H7N9 virus vaccine (2017 A/H7N9 IIV) manufactured by Sanofi Pasteur (SP), administered intramuscularly (IM) at 3.75 mcg hemagglutinin (HA) per dose, given with or without AS03 adjuvant manufactured by GlaxoSmithKline Biologicals (GSK), to subjects primed with a monovalent inactivated split influenza 2013 A/H7N9 virus vaccine (2013 A/H7N9 IIV) in DMID Protocols 13-0032 and 13-0033, or to those who are A/H7 IIV-naïve. Phosphate buffered saline (PBS) diluent manufactured by Patheon Manufacturing Services LLC will be used to achieve the targeted dosage.

Subjects who received the 2013 A/H7N9 IIV in DMID Protocols 13-0032 and 13-0033 or are A/H7 IIV-naïve will be stratified by prior receipt of 2013 A/H7N9 IIV, as well as by site and prior receipt of licensed, seasonal influenza vaccine (defined as receipt of at least one of the 2017-2018 and/or 2018-2019 licensed, seasonal influenza vaccines versus none), then randomly assigned in a 1:1 ratio to 1 of 2 treatment arms to receive 1 dose of 2017 A/H7N9 IIV at 3.75 mcg HA per dose with or without AS03 adjuvant (see Table 1).

Reactogenicity will be measured by the occurrence of solicited injection site and systemic reactions from the time of study vaccination through 7 days after study vaccination. Unsolicited non-serious adverse events (AEs) will be collected from the time of study vaccination through approximately 21 days after study vaccination. Serious adverse events (SAEs) and medically-attended adverse events (MAAEs), including new-onset chronic medical conditions (NOCMCs) and potentially immune-mediated medical conditions (PIMMCs), will be collected from the time of study vaccination through approximately 12 months after study vaccination. Clinical safety laboratory evaluations (hematology and chemistry) will be performed on venous blood collected immediately prior to study vaccination and approximately 7 days after study vaccination.

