## 5. SAMPLE SIZE CONSIDERATIONS

This study is planned to enroll up to 420 subjects. The majority of subjects will be recruited from the population of subjects who received the 2013 A/H7N9 IIV in DMID Protocols 13-0032 and 13-0033. The sample size for this study was selected using estimates of recruitment based on the number of subjects completing these historical protocols and by 2013 A/H7N9 IIV vaccination history. [Table 4](#) summarizes the vaccination history in these protocols and potential enrollment into this study. While this study is not designed to test any specific null hypothesis, the following tables illustrate the precision and power that is available for select estimates and comparisons of interest.

[Table 5](#) indicates the probability of observing one or more safety events, such as solicited injection site or systemic reactogenicity events or an unsolicited non-serious AE of a particular type for treatment arms (N=30, 50), in all subjects receiving adjuvant (N=210) or in the trial as a whole (N=420).

Binomial confidence intervals (CIs) are widest (have the least precision) when the response rate is 50%. [Table 6](#) is presented to indicate the worst-case scenario for precision of observed exact (Clopper-Pearson) binomial confidence intervals.

[Table 7](#) illustrates the minimum detectable differences in the proportion of subjects responding (e.g. attaining seroconversion or a titer  $\geq 40$ ) between any two treatment arms (N=30 or 50) using a two-sided Likelihood Ratio Test with  $\alpha = 0.05$ . From previous experience with single dose studies, it is assumed that up to 3% of subjects will be excluded from the per protocol analysis with minimal effect on these calculations. Seroconversion rates of 10% to 90% are considered.

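### The N=30, 90%-responder row of Protocol Table 13 and SAP Table 7 claims 80% power, but no higher comparator rate gives more than 58.9%

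*Protocol*

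**What the plan says.** Protocol 11.4.3 introduces Table 13 as showing minimum detectable differences in the proportion of responders "between any two treatment arms (N=30 or 50) using a two-sided Likelihood Ratio Test and alpha = 0.05". The results column is headed 80% power. SAP Section 5 says of its Table 7, which has the same entries, that it "illustrates the minimum detectable differences in the proportion of subjects responding", again "using a two-sided Likelihood Ratio Test with" alpha 0.05.

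Two rows matter here:

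- N=30, Group A at 0.90: "0.90 0.10 >0.99", that is, a detectable difference of 0.10 and a Group B rate above 0.99. The N=50 block has a row with the same three values.
- N=50, Group A at 0.80: "0.80 0.17 0.96".

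The arms with 30 subjects are 7 to 10 in Protocol Table 1 (the mixed-prime and A/H7 IIV-naïve strata), for example "9/30 2017 A/H7N9 IIV 3.75 mcg + AS03". Protocol 11.4.3 also limits what the table is for: "While this study is not designed to test any specific null hypothesis, the following illustrates the precision and power that are available".

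**The concern.** For a lower rate of 0.90, the largest upward difference possible is 1.00 − 0.90 = 0.10. An entry of 0.10 with a comparator above 0.99 therefore sits at the ceiling. It looks like the boundary value, not a solution of the power equation, and the same entry appears at both sample sizes although power at N=30 must be lower than at N=50.

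Protocol 11.2 refers readers to Section 11.4.3 for the comparisons that the sample size can support. If the entry is wrong, a reader comparing two high-responding 30-subject arms would credit the design with 80% power that it does not have, and could read too much into a non-significant result.

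The N=50, 0.80 row raised a smaller question, because its difference and its comparator rate do not add up.

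**Working it through.** **Inputs.** 30 and 50 per arm, likelihood ratio test, two-sided, alpha 0.05, 80% power (Protocol 11.4.3 and Table 13; SAP Section 5 and Table 7). Equal arms, because subjects are "randomly assigned in a 1:1 ratio to 1 of 2 treatment arms" (Protocol Section 4). Up to 3% exclusions from the per protocol analysis (Protocol 11.4.3), which takes 30 to about 29.

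**Method.** For responder counts a and b out of n per arm, G² = 2 Σ O ln(O/E), with E from the pooled proportion. Reject when G² exceeds 3.841 (chi-square, 1 df). Power is the sum of the two binomial probabilities over all outcomes that reject.

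**Reproducing the table.** Exact power at each printed Group B rate:

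| Group A | N=30: printed B | Power | N=50: printed B | Power |
|---|---|---|---|---|
| 0.10 | 0.39 | 80.0% | 0.32 | 80.0% |
| 0.20 | 0.54 | 80.7% | 0.46 | 80.1% |
| 0.30 | 0.65 | 79.8% | 0.57 | 80.0% |
| 0.40 | 0.75 | 80.6% | 0.67 | 79.8% |
| 0.50 | 0.83 | 81.0% | 0.77 | 81.3% |
| 0.60 | 0.90 | 82.2% | 0.85 | 81.9% |
| 0.70 | 0.95 | 80.0% | 0.92 | 83.8% |
| 0.80 | 0.99 | 84.4% | 0.96 | **75.9%** |
| 0.90 | >0.99 (at 1.00) | **58.9%** | >0.99 (at 1.00) | 88.8% |

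The method reproduces the table except for the two entries in bold.

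**N=30, Group A at 0.90.** Take Group B at its best, 30 of 30.

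- 2 non-responders in Group A (28 v 30; expected 29 responders and 1 non-responder per arm): G² = 2[28 ln(28/29) + 30 ln(30/29) + 2 ln(2/1)] = 2(−0.983 + 1.017 + 1.386) = 2.84. Not rejected.
- 3 non-responders (27 v 30; expected 28.5 and 1.5): G² = 2[27 ln(27/28.5) + 30 ln(30/28.5) + 3 ln(3/1.5)] = 2(−1.460 + 1.539 + 2.079) = 4.32. Rejected.

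Power at B = 1.00 is therefore P(X ≥ 3), where X is binomial with n = 30 and p = 0.10: 1 − (0.0424 + 0.1413 + 0.2277) = 0.5886.

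Across the printed range for B, power is 45.2% at 0.99, 51.6% at 0.995, 57.3% at 0.999 and 58.9% at 1.00, which is the maximum. With 29 per arm the maximum is 56.5%.

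- For 0.90 v 1.00, 41 per arm gives 79.1% and 42 gives 80.5%.
- At 30 per arm, 80% power against a comparator of 1.00 requires Group A to be no higher than 0.863.

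**N=50, Group A at 0.90.** Power reaches 80% at B = 0.996 and 88.8% at B = 1.00, so this entry is attainable.

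**N=50, Group A at 0.80.** 0.80 + 0.17 = 0.97, not 0.96. Power is 75.9% at B = 0.96 and 83.8% at B = 0.97; exactly 80% falls at B = 0.965. The printed difference is right to two decimals and the printed B is one unit low in its last digit.

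**The case against.** **The direction of the difference.** The test is two-sided, and with Group A at 0.90 power does reach 80% at a lower comparator of about 0.61. That is a difference of about 0.29, not 0.10, and every row of the table takes Group B above Group A. The claim is that no higher rate reaches 80%, and the corrected cell should say so.

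**The method is inferred.** Neither document says that power was enumerated exactly. Exact enumeration fits the rest of the table, and the conclusion does not depend on it. At B = 1.00 with 30 per arm, the noncentral chi-square approximation to the likelihood ratio test gives 54.7%, the Fleiss formula 42.5%, Pearson and Wald 35.3%, and Yates and Fisher 7.3%. Only a one-sided 0.05 likelihood ratio test passes 80% (81.6%), and the plan states a two-sided one. What stands is that clearing the N=50, 0.90 row does depend on the method: the noncentral approximation peaks at 76.5% there.

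**The N=50, 0.80 slip may be noise.** Other rows also differ from the exact solution by up to 0.01, for example N=30 at 0.60 and N=50 at 0.70. Those two are rounded up: one step lower in B gives 78.7% and 78.9%. The 0.80 row differs because its two printed numbers contradict each other.

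**The consequence is small.** This stands. The table is illustrative, SAP 8.1 plans no formal hypothesis test, and the cell matters only if the lower of two 30-subject arms exceeds about 86% responders. Protocol 2.1 describes A/H7 vaccines as poorly immunogenic, which makes that unlikely.

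**Conclusion.** The concern holds. In both documents the N=30, 0.90 row states 80% power where the stated test gives between 45.2% (B = 0.99) and 58.9% (B = 1.00), or at most 56.5% after the plan's own exclusion allowance. These figures rest on equal arms and on exact binomial enumeration of a two-sided likelihood ratio test at alpha 0.05; the other two-sided methods tried give less.

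The N=50, 0.80 row has a last-digit error in Group B and no real loss of power. The other 16 rows hold under exact enumeration.

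No conclusion about the sample size follows, because it was set from recruitment estimates. The point is worth correcting because a published power figure is false, not because the design fails.

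**What to change.** In Protocol Table 13 and SAP Table 7:

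1. Replace the N=30, 0.90 entry with a statement that 80% power is not attainable for any higher comparator rate (maximum power 59%).
2. In the N=50, 0.80 row, change Group B from 0.96 to 0.97, to agree with the printed difference of 0.17.

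It would also help to note under each table that power was obtained by exact enumeration, if that is what was done, since the N=50, 0.90 row depends on it.

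The cost is two table rows in each document, plus the optional note. Sample size, conduct and analysis are unaffected.
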